5.2.2 Subject Disposition

The number and percentage of subjects who completed extension phase and discontinued the study, and reasons for discontinuation will be summarized for each treatment group and overall.

5.2.3 Protocol Deviations

Major protocol deviation criteria will be established and subjects with major protocol deviations will be identified and documented before the database lock. The protocol deviations identified according to the criteria at study entry and during treatment will not be included in tables, listings, and graphs (TLGs) covered by SAP, but presented in the clinical study report (CSR).

5.2.4 Demographic and Other Baseline Characteristics

Demographic and other baseline characteristics for the Safety Analysis Set and FAS will be summarized for each treatment group and overall using descriptive statistics.

Continuous demographic and baseline variables include:

- Age (year)
- Height (cm)
- Weight (kg)
- BMI (kg/m^2) at Screening
- Rheumatoid Arthritis (RA) Duration (years)
- Dose of MTX (mg/week)
- Serum Rheumatoid Factor (RF) Concentration (IU/mL)

- Serum Anti-Cyclic Citrullinated Peptide (CCP) Antibody Concentration (U/mL)
- Oral Steroid*¹ (mg/day)
- ACR Components
 - TJC68 at Baseline
 - SJC66 at Baseline
 - TJC28 at Baseline
 - SJC28 at Baseline
 - CRP (mg/dL) at Screening
 - CRP (mg/dL) at Baseline
 - ESR (mm/h) at Baseline
 - Physician's Global Assessment of Disease Activity (VAS) (mm) at Baseline
 - Patient's Global Assessment of Disease Activity (VAS) (mm) at Baseline
 - Patient's Assessment of Pain (VAS) (mm) at Baseline
 - HAQ-DI at Baseline
- DAS28-CRP at Baseline
- DAS28-ESR at Baseline
- CDAI at Baseline
- SDAI at Baseline
- Joint Space Narrowing at Baseline
- Number of Bone Erosions at Baseline
- mTSS at Baseline
- mTSS divided by RA Duration (/year)

Categorical variables include:

- Age group (18<= <35, 35<= <50, 50<= <75)
- Sex (Male, Female)
- Ethnicity (Hispanic or Latino, Not Hispanic or Latino)
- Race (White, Black or African American, Japanese, Chinese, Other Asian, American Indian or Alaska Native, Native Hawaiian or Other Pacific Islander, Other)
- RA Duration (< 5 years, 5 years <=)
- RA Duration (< 1 year, 1 year <= < 5 years, 5 years <= < 10 years, 10 years <= < 15 years, >= 15 years)

- Smoking History (Current, Former, Never)
- Current Medical Conditions (Yes, No)
- Prior Use of Biologics Treatment (Yes - TNF*²/Non-TNF, No)
- Drug experience of MTX (Yes, No)
- Dose of MTX (< 6 mg/week, 6 mg/week <= < 12 mg/week, >= 12 mg/week)
- Drug experience of DMARDs within 12 weeks before informed consent except MTX (Yes - 1/2/..., No)
- Continuation of Steroid
- Serum RF Concentration (Seropositive - High Positive/Low Positive, Seronegative)*³
- Anti-CCP Antibody (Seropositive - High Positive/Low Positive, Seronegative)*⁴
- Classification of Global Functional Status in RA
- DAS28-CRP Category (High: >4.1, Moderate: 2.7 <= < 4.1, Low: <= 2.7)
- DAS28-ESR Category (High: >5.1, Moderate: 3.2 <= < 5.1, Low: <= 3.2)
- CDAI (High: > 22, Moderate: 10 <= < 22, Low: <= 10)
- SDAI (High: > 26, Moderate: 11 <= < 26, Low: <= 11)
- CRP level at Screening (< 0.6mg/dL, >= 0.6mg/dL)
- CRP level at Baseline (< 0.6mg/dL, >= 0.6mg/dL)
- ESR level at Baseline (< 28mm/h, >= 28mm/h)

*1 Prednisone-equivalent dose

*2 Refer section 8.5 “TNF agent”

*3 Categories of Serum RF Concentration are derives as follows:

Seropositive: > 15 (IU/mL)

High Positive: < 45 (IU/mL)

Low Positive: 15 <= < 45 (IU/mL)

Seronegative: <= 15 (IU/mL)

*4 Categories of Anti-CCP Antibody are derives as follows:

Seropositive: >= 4.5 (U/mL)

High Positive: < 13.5 (U/mL)

Low Positive: 4.5 <= < 13.5 (U/mL)

Seronegative: < 4.5 (U/mL)

Subject data listings will be provided.

MEDICAL HISTORY

A subject data listing will be provided.

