9.7.1.1.2 SECONDARY ENDPOINTS

- ACR20, ACR50, and ACR70 response rates at each evaluation time point (excluding ACR20 response rate at Week 12)
- Values and change from baseline in ACR components (number of tender joints, number of swollen joints, VAS [Patient's pain assessments/disease activity global assessments and physician's disease activity global assessment], patient's physical function assessment [HAQ], and CRP/ESR), DAS28-ESR, DAS28-CRP, SDAI, and CDAI at each evaluation time point
- EULAR response criteria and disease activity classification based on DAS28-ESR or DAS28-CRP at each evaluation time point
- Remission rate calculated based on each remission criterion (DAS28-ESR, DAS28-CRP, SDAI, CDAI, and Boolean) at each evaluation time point
- Values and change from baseline in mTSS at each evaluation time point

The ACR50 response rate is defined similarly to the ACR20 response rate, except for a 50% reduction as threshold.

The ACR70 response rate is defined similarly to the ACR20 response rate, except for a 70% reduction as threshold.

DAS28-CRP: This will be calculated on the following formula, and disease activity is categorized as High at >4.1 , Moderate at >2.7 and ≤ 4.1 , Low at ≤ 2.7 , and Remission at <2.3 .

$$0.56 \times \sqrt{[\text{Number of tender joints (28 joints)}]} + 0.28 \times \sqrt{[\text{Number of swollen joints (28 joints)}]} + 0.36 \times \ln(\text{CRP} \times 10 + 1) + 0.014 \times \text{Patient's disease activity assessments} + 0.96$$

DAS28-ESR: This will be calculated on the following formula, and disease activity is categorized as High at >5.1 , Moderate at >3.2 and ≤ 5.1 , Low at ≤ 3.2 , and Remission at <2.6 .

$$0.56 \times \sqrt{[\text{Number of tender joints (28 joints)}]} + 0.28 \times \sqrt{[\text{Number of swollen joints (28 joints)}]} + 0.70 \times \ln(\text{ESR}) + 0.014 \times \text{Patient's disease activity assessments}$$

EULAR Response Criteria:

Present DAS28	DAS28 reduction from baseline		
	<-1.2	≥-1.2 and <-0.6	≥-0.6 (missing included)
Low	Good response	Moderate response	No response
Moderate	Moderate response	Moderate response	No response
High	Moderate response	No response	No response

The CDAI will be calculated on the following formula, and disease activity is categorized as High at >22 , Moderate at >10 and ≤ 22 , Low at ≤ 10 , and Remission at ≤ 2.8 .

Number of swollen joints (28 joints) + Number of tender joints (28 joints)
+ Patient's disease activity assessments/10

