5.1.2 Secondary Endpoints

- ACR20, ACR50, and ACR70 response rate at each visit (excluding ACR20 at Week 12)
- Values and change from baseline in ACR components (TJC, SJC, VAS [patient's assessment of pain, patient's global assessment of disease activity and physician's global assessment of disease activity], functional assessment by subjects [HAQ-DI], and CRP·ESR), DAS28-ESR, DAS28-CRP, SDAI, and CDAI at each visit
- EULAR response criteria at each visit; subjects will be classified based on DAS28-ESR or DAS28-CRP
- DAS28-ESR, DAS28-CRP, SDAI, CDAI, and Boolean remission rates at each visit
- Values and change from baseline in modified total sharp score (mTSS) at each visit

The ACR50 response is defined similar to the ACR20 with a 50% reduction.

The ACR70 response is defined similar to the ACR20 with a 70% reduction.

The DAS28-CRP calculates on the following formula, and disease activity is categorized as High at > 4.1 , Moderate at > 2.7 and ≤ 4.1 , Low at ≤ 2.7 , and Remission at ≤ 2.3 .

$$0.56 \times \text{sqrt}\{\text{TJC in 28 joints (TJC28)}\} + 0.28 \times \text{sqrt}\{\text{SJC in 28 joints (SJC28)}\} + 0.36 \times \ln\{\text{CRP (mg/dL)} \times 10 + 1\} + 0.014 \times \text{Patient's Global Assessment of Disease Activity (VAS) (mm)} + 0.96$$

The DAS28-ESR will be calculated on the following formula, and disease activity is categorized as High at > 5.1 , Moderate at > 3.2 and ≤ 5.1 , Low at ≤ 3.2 , and Remission at < 2.6 .

$$0.56 \times \text{sqrt}\{\text{TJC28}\} + 0.28 \times \text{sqrt}\{\text{SJC28}\} + 0.70 \times \ln\{\text{ESR (mm/h)}\} + 0.014 \times \text{Patient's Global Assessment of Disease Activity (VAS) (mm)}$$

EULAR Response Criteria:

Present DAS28	DAS28 change from baseline		
	<-1.2	≥ -1.2 and <-0.6	≥ -0.6 (missing included)
Low	Good response	Moderate response	No response
Moderate	Moderate response	Moderate response	No response
High	Moderate response	No response	No response

The CDAI will be calculated on the following formula, and disease activity is categorized as High at > 22 , Moderate at > 10 and ≤ 22 , Low at ≤ 10 , and Remission at ≤ 2.8 .

$$\begin{aligned} & \text{SJC28} + \text{TJC28} \\ & + \text{Patient's Global Assessment of Disease Activity (VAS) (mm)/10} \\ & + \text{Physician's Global Assessment of Disease Activity (VAS) (mm)/10} \end{aligned}$$

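### SAP 5.2.4 reverses the inequality for the High Positive RF and anti-CCP classes, so high-titre subjects have no sub-category in the Extension Phase baseline table

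*SAP*

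**What the plan says.** SAP 5.2.4 lists RF and anti-CCP among the categorical baseline variables. Each has a Seropositive class, split into High and Low Positive, and a Seronegative class. Notes *3 and *4 give the derivations.

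- RF: "Seropositive: > 15 (IU/mL", "High Positive: < 45 (IU/mL", "Low Positive: 15 <= < 45 (IU/mL" and "Seronegative: <= 15 (IU/mL" (each in IU/mL).
- Anti-CCP: Seropositive from 4.5 U/mL upwards, "High Positive: < 13.5 (U/mL", Low Positive from 4.5 up to but not including 13.5, and Seronegative below 4.5.

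The same section gives baseline disease-activity classes, for example "DAS28-CRP Category (High: >4.1, Moderate: 2.7 <= < 4.1, Low: <= 2.7". DAS28-ESR, CDAI and SDAI follow the same pattern. SAP 5.1.2 and protocol 9.7.1.1.2 define these classes differently: Moderate lies above the lower cut and includes the upper cut.

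For DAS28-CRP, SAP 5.1.2 has "Remission at ≤ 2.3" and protocol 9.7.1.1.2 has "Remission at <2.3". SAP section 7, which lists departures from the protocol, does not mention this.

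**The concern.** Notes *3 and *4 are derivation rules that a programmer is meant to follow. A high-titre class defined by an upper limit cannot separate high from low titres, so the sub-rows would describe the wrong subjects and omit the ones they are named for. The programmer must either follow an unusable rule or depart from the SAP without a record.

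The disease-activity bounds raise a smaller issue of the same kind. The SAP holds two versions of the same classes, and SAP 5.4.2 also plans shift tables of those classes. A subject exactly on a cut could be placed differently in the baseline table and in the shift table. For DAS28-CRP remission, which is a secondary endpoint, the protocol and SAP give two definitions.

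**Working it through.** The plan states no figure to reproduce here. The check is to apply each rule as written to values on, above and below each cut.

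**Serology.** Inputs are the cut-offs in SAP 5.2.4, notes *3 and *4. High and Low Positive are treated as sub-classes of Seropositive, which is how the variable list sets them out.

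| Value | Seropositive? | Sub-class as written | Sub-class with the sign corrected |
|---|---|---|---|
| RF 5 | no | not applicable | not applicable |
| RF 15 | no (15 is not > 15) | not applicable | not applicable |
| RF 30 | yes | High and Low | Low |
| RF 45 | yes | none | High |
| RF 200 | yes | none | High |
| Anti-CCP 1 | no | not applicable | not applicable |
| Anti-CCP 10 | yes | High and Low | Low |
| Anti-CCP 13.5 | yes | none | High |
| Anti-CCP 100 | yes | none | High |

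Within Seropositive, High Positive as written means 15 < RF < 45 and 4.5 <= anti-CCP < 13.5. Those are the Low Positive ranges. Nothing covers RF >= 45 or anti-CCP >= 13.5.

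The intended bounds can be inferred. The Low Positive ranges stop just short of 45 and 13.5, so only >= 45 and >= 13.5 complete the split without overlap. The ratios fit: 45/15 = 3 and 13.5/4.5 = 3.

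**Disease-activity classes.** Under SAP 5.2.4, Low is <= lower cut, Moderate is >= lower and < upper, and High is > upper. Under SAP 5.1.2 and the protocol, Moderate is > lower and <= upper.

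| Score | Lower cut: 5.2.4 | Lower cut: 5.1.2 | Upper cut: 5.2.4 | Upper cut: 5.1.2 |
|---|---|---|---|---|
| DAS28-CRP | 2.7: Low and Moderate | Low | 4.1: none | Moderate |
| DAS28-ESR | 3.2: Low and Moderate | Low | 5.1: none | Moderate |
| CDAI | 10: Low and Moderate | Low | 22: none | Moderate |
| SDAI | 11: Low and Moderate | Low | 26: none | Moderate |

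Only exact cut values differ, but some can be reached. With 2 swollen joints, 2 tender joints and both global VAS scores at 30 mm, CDAI = 2 + 2 + 3 + 3 = 10. With 6, 6, 50 mm and 50 mm, CDAI = 6 + 6 + 5 + 5 = 22.

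**DAS28-CRP remission.** The two definitions differ only at a score of exactly 2.3. Using the formula in SAP 5.1.2:

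- At CRP = 0 the log term is zero, so equality needs 0.56 sqrt(TJC28) + 0.28 sqrt(SJC28) + 0.014 VAS = 2.3 - 0.96 = 1.34. Dividing by 0.014 gives 40 sqrt(TJC28) + 20 sqrt(SJC28) + VAS = 670/7. With whole-number counts and VAS in whole mm, the left side can be rational only if it is an integer. Since 670/7 is not an integer, there is no solution.
- At any recorded CRP above 0, the log term rules out equality.
- After rounding to 2 decimals, 2.30 does occur. A grid over all 28-joint counts, VAS 0 to 100 mm and CRP 0 to 5 mg/dL in steps of 0.01 gives 1,107 such combinations out of 42,555,441. This shows that the value can be reached; it is not an estimate of how often patients have it.

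SAP 8.4 sets 2 decimals for these scores when reporting descriptive statistics, but does not say whether they are rounded before classification.

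**The case against.** The strongest reply is that this is a typographical slip in two descriptive sub-rows, and that several larger conclusions a reader might draw do not follow. Most of that reply stands.

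- *Seronegative subjects counted as High Positive, and RF = 15 placed in two classes.* Taken one by one, the lines do say this. The variable list, however, nests High and Low under Seropositive, and a subject who fails the parent condition never reaches either. The lower limit of RF Low Positive is untidy but harmless.
- *Inclusion criterion 7 compromised.* That criterion uses positive or negative serology, not titre class. The two-way split in the notes is complete and does not overlap.
- *Balance of the randomised groups obscured.* This SAP covers the Extension Phase, and SAP 5.2.1 requires dosing and assessment after Week 24. Its baseline table describes subjects who continued. Protocol 9.7 also provides for a Treatment Phase plan; that plan is not among the documents, so we cannot say whether it carries the error.
- *Remission counts wrong in general.* The DAS28-ESR, CDAI, SDAI and Boolean definitions agree between protocol and SAP. Only DAS28-CRP differs, and only for a score rounded to 2.30.
- *Titre information lost.* RF and anti-CCP are also summarised as continuous variables, and listings are planned.

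Programming specifications and table shells are separate documents (SAP sections 9 and 11), so the programs may already use the right sign. None of this rescues the rule as written: even under the nested reading, High repeats Low and the high titres have no class. A fault in text extraction is unlikely, because both notes show the same reversal while other greater-than signs in them are intact.

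**Conclusion.** The High Positive definitions are wrong as written. Within Seropositive, every low-titre subject meets both sub-classes, and every subject with RF >= 45 or anti-CCP >= 13.5 meets neither. The documents give no baseline serology, so the number of subjects cannot be stated. Subjects without a sub-class still count as Seropositive.

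The consequence is minor and limited to description. The SAP plans no covariates, subgroups or primary analysis for the Extension Phase (SAP 5.3.2, 5.3.4 and 5.4.1), and titre class is not an allocation factor. The Week 12 ACR20 comparison is not touched.

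The disease-activity bounds are a real but smaller inconsistency, confined to exact cut values. The DAS28-CRP remission mismatch has no effect on unrounded scores and needs only reconciling.

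The conclusion assumes that tables are programmed from the SAP text and that High and Low Positive are sub-classes of Seropositive. The corrected bounds are inferred; neither document states them.

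**What to change.** In SAP 5.2.4:

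1. Set RF High Positive to >= 45 IU/mL and anti-CCP High Positive to >= 13.5 U/mL.
2. Set RF Low Positive to > 15 and < 45, to match its parent class. Anti-CCP Low Positive can stay as it is.
3. Replace the baseline DAS28-CRP, DAS28-ESR, CDAI and SDAI bounds with those of SAP 5.1.2, or refer to that section.

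Elsewhere in the SAP:

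4. Reconcile the DAS28-CRP remission cut with the protocol, or list the difference as a change in SAP section 7.
5. State whether scores are rounded before they are classified.

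The cost is a few characters in 5.2.4 and a sentence or two elsewhere, with no new data or analysis. If the tables already exist, check the cut-offs actually programmed and record them in the clinical study report.

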5.2.5 Prior and Concomitant Therapy

All investigator terms for medications recorded in the case report form (CRF) will be coded to an 11-digit code using the World Health Organization Drug Dictionary (WHO DD) version (Mar2016 or later). The number (percentage) of subjects who took prior and concomitant medications will be summarized on the FAS by treatment group, Anatomical Therapeutic Chemical (ATC) class, and WHO DD preferred term. Prior medications will be defined as medications that stopped before the first dose of study drug. Concomitant medications will be defined as medications that (1) started before the first dose of study drug and were continuing at the time of the first dose of study drug, or (2) started on or after the date of the first dose of study drug. A subject data listing of all medications will be provided.

5.2.6 Treatment Compliance

Treatment compliance will be described in [section 5.6.1](#).

5.3 Data Analysis General Considerations

5.3.1 Pooling of Centers

Subjects from all centers will be pooled for all analyses.

5.3.2 Adjustments for Covariates

No covariates are planned for analyses for extension phase.

5.3.3 Multiple Comparisons/Multiplicity

No multiplicity are planned for analyses for extension phase.

5.3.4 Examination of Subgroups

No subgroup analyses are planned for analyses for extension phase.

5.3.5 Handling of Missing Data, Dropouts, and Outliers

For the efficacy analyses, approaches to handling missing data for continuous variables, except mTSS, will be the observed cases (OC) method and the last observation carried forward (LOCF) method; binary variables and EULAR response criteria will be the observed cases (OC) method, the last observation carried forward (LOCF) method and the non-responder imputation (NRI) method as each visit.

mTSS value at Week 24, Week 52 and Week 76 will be extrapolated from values of baseline and values of postbaseline, which will be used in summary statistics. The linear extrapolation method will be used for analysis of the structural progression endpoint (van der Heijde mTSS) to impute missing data at time points when analyses are conducted (including the analyses at Week 24, Week 52 and Week 76). For patients who discontinue the study or the study treatment or for patients who miss a radiograph for any reason, baseline data and the most recent radiographic data prior to discontinuation or the missed radiograph, adjusted for time, will be used for linear extrapolation to impute missing data at subsequent time points. All patients originally randomized to placebo will be switched to active treatment at Week 24; Missing postbaseline values will be imputed only if both a baseline value and a postbaseline value from another time point are available, as long as the patient was on the same treatment at each applicable time point.

Calculation for value of mTSS extrapolation will be derived by follow formula:

- Week 24 = (Postbaseline) + (Postbaseline – Baseline) * ((24 – (Study Day of Postbaseline / 7) / Study Day of Postbaseline / 7)
- Week 52 = (Postbaseline) + (Postbaseline – Baseline) * ((52 – (Study Day of Postbaseline / 7) / Study Day of Postbaseline / 7)
- Week 76 = (Postbaseline) + (Postbaseline – Baseline) * ((76 – (Study Day of Postbaseline / 7) / Study Day of Postbaseline / 7)

The two individual components of mTSS (Erosion and joint space narrowing [JSN] score) will be analyzed in the same way as the mTSS.

For the safety analyses for continuous value, descriptive statistics are used OC method and LOCF method, this is applied only the last observation of each phase, in tables and figures.

In the cases of laboratory result contains less (or more) than quantitation limit value is treated as:

- a. zero, when less than quantitation limit value,
- b. quantitation limit value, when more than quantitation limit value.

In the cases of pharmacokinetic data, refer "[8.2 Convention for Pharmacokinetic data handling](#)".

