9.1.1 Screening Phase

Subjects must be fully informed of the nature of the study and written informed consent must be obtained prior to the start of any assessment/evaluation for this study. The procedure for obtaining informed consent is described in [Section 5.3](#).

Subjects who submitted informed consent will undergo screening evaluations between Day -42 and Day -1 to confirm that each subject meets all the inclusion criteria and none of the exclusion criteria.

Results of the screening assessments will be recorded in the CRF. If a subject is judged ineligible to enroll the study, the reason should also be recorded in the CRF.

For subjects who require prophylactic treatments with isoniazid based on the results of the tuberculosis test at the Screening Phase, the prophylactic treatments are needed for at least 21 days before starting the study treatment, so the duration of the Screening Phase may be extended until 21 days from the start of isoniazid administrations. If a patient requires another syphilis test based on the result in the Screening Phase, reexamination has to be performed after an interval of 21 days or longer during the Screening Phase. The Screening Phase can be extended until the reexamination result is obtained.

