9.5.1.3.6 ASSESSMENT OF JOINT X-RAY

Joint x-ray images will be captured in the Screening Phase, Treatment Phase (Week 24), Extension Phase (Weeks 52, 76, and 104), and at discontinuation.

Joint x-ray images will be sent to the institute of joint x-ray central evaluation with subject identification number. The institute will evaluate the images, and the evaluation results of joint x-ray images captured by Week 24 will be submitted to the sponsor after unblinding. Joint x-ray images will be evaluated according to the separately prescribed procedures.

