8 DEFINITIONS AND CONVENTIONS FOR DATA HANDLING

8.1 Baseline, Time Windows for statistical analyses

8.1.1 Definition of baseline value

The baseline value was defined as the most recent value reported just before first dosing.

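### SAP 5.3.5: the mTSS extrapolation ignores the weeks between the Screening film and first dose, so every non-zero forward-extrapolated change is too large in magnitude

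*SAP*

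**What the plan says.** SAP 5.3.5 imputes missing mTSS values at Weeks 24, 52 and 76 by linear extrapolation: "baseline data and the most recent radiographic data prior to discontinuation or the missed radiograph, adjusted for time, will be used for linear extrapolation". The Week 52 line begins "Week 52 = (Postbaseline) + (Postbaseline – Baseline) * ((52 – (Study Day of Postbaseline / 7) / Study Day of Postbaseline / 7" and is then closed by a single bracket, so three brackets open and two close in the last factor. The Week 24 and Week 76 lines have the same form. Imputation needs a baseline and another post-baseline value, "as long as the patient was on the same treatment at each applicable time point". The erosion and joint space narrowing scores are handled in the same way.

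Protocol 9.5.1.3.6 fixes when films are taken: "Joint x-ray images will be captured in the Screening Phase, Treatment Phase (Week 24), Extension Phase (Weeks 52, 76, and 104), and at discontinuation". Protocol Table 4 shows no joint x-ray in the Observation Phase. SAP 8.1.1 states: "The baseline value was defined as the most recent value reported just before first dosing". The baseline mTSS is therefore read from the Screening film. Under Protocol 9.1.1, subjects "will undergo screening evaluations between Day -42 and Day -1". The phase may be lengthened for isoniazid prophylaxis or for a repeat syphilis test; for the latter, "The Screening Phase can be extended until the reexamination result is obtained".

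**The concern.** The text promises an adjustment for time, but no term in the formula carries the date of the baseline film. The observed change built up over the interval from the Screening film to the last film. The formula divides it by the shorter interval from first dose to the last film, and the overstated weekly rate is then carried forward to the target week.

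A subject with an observed Week 52 film contributes a change measured from the Screening film, that is, over 52 + s weeks. An imputed subject with the same linear course is given a larger change. Both enter the same summaries, and SAP 5.4.2 also plans cumulative probability displays of mTSS change at Weeks 52 and 76. Repairing the brackets does not remove the discrepancy.

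**Working it through.** The documents give no numerical result for the extrapolation, so there is no plan figure to reproduce.

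**Inputs**
- t: weeks from first dose to the last available film, read as Study Day / 7. Study Day is not defined for mTSS. First dose as origin is inferred from SAP 5.6, which sets Day 1 at first dose for safety analyses, and from SAP Table 8.12, which counts x-ray visits from first administration.
- s: weeks from the baseline film to first dose. The standard window of Day -42 to Day -1 gives about 0.14 to 6 weeks. No maximum is given for an extended Screening Phase; s = 9 is used below as an assumption.
- W: target week (24, 52 or 76).

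**Formulas**, with brackets read as (W - t)/t
- SAP: Post + (Post - Base) x (W - t)/t = Base + (Post - Base) x W/t. This places the baseline film at time 0.
- Actual film interval: Base + (Post - Base) x (W + s)/(t + s).
- Ratio of the two changes: W(t + s)/[t(W + s)]. It exceeds 1 whenever s > 0 and W > t.

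**Last film at Week 24, s = 6**
- Week 52: SAP multiplier 52/24 = 2.167; film-interval multiplier 58/30 = 1.933; ratio 1.121.
- Week 76: 76/24 = 3.167 against 82/30 = 2.733; ratio 1.159.

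**Last film at Week 24, s = 3**
- Week 52: (52 x 27)/(24 x 55) = 1404/1320 = 1.064.
- Week 76: (76 x 27)/(24 x 79) = 2052/1896 = 1.082.

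**Last film at Week 52, target Week 76, s = 6**
- (76 x 58)/(52 x 82) = 4408/4264 = 1.034.

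**Excess in the magnitude of the change, by s**

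| Last film to target | 1 day | 2 wk | 4 wk | 6 wk | 9 wk (assumed) |
|---|---|---|---|---|---|
| Week 24 to 52 | 0.3% | 4.3% | 8.3% | 12.1% | 17.2% |
| Week 24 to 76 | 0.4% | 5.6% | 10.8% | 15.9% | 22.9% |
| Week 52 to 76 | 0.1% | 1.2% | 2.3% | 3.4% | 4.9% |

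Counting the Week 24 film as Study Day 169 (24.14 weeks) moves the s = 6 figures only to 11.9% and 15.7%.

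**Direction** (illustrative changes, last film at Week 24, s = 6)

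| Observed change | Week 52: SAP / film interval | Week 76: SAP / film interval |
|---|---|---|
| +2 | +4.33 / +3.87 | +6.33 / +5.47 |
| 0 | 0 / 0 | 0 / 0 |
| -2 | -4.33 / -3.87 | -6.33 / -5.47 |

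**Week 24.** The same formula applies. With a discontinuation film at Week 12 (assumed) and s = 6, the ratio is (24 x 18)/(12 x 30) = 1.20.

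**The case against.** The case for leaving the rule alone is mainly about size and consequence, and much of it stands.

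- **The worst figures need unusual circumstances.** Subjects who discontinue should have a film at that point, and the SAP 5.2.1 FAS requires dosing and an efficacy measurement from Week 24 on. A last film at Week 24 therefore implies very early extension dropout or a missed film. The same FAS rule means the Week 24 formula should seldom matter here. Each percentage applies to an individual imputed value and is diluted in a group mean.
- **Nothing confirmatory depends on it.** This SAP covers the Extension Phase and plans no primary efficacy analysis, covariates or multiplicity adjustment there. The radiographic objective is at Week 24.
- **The time origin is an inference.** SAP section 9 leaves derivation rules to separate documents, and the Week 0 row of Table 8.12 is unclear. This is a reason to define the origin; it does not supply the missing baseline film date.

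Two stronger readings are tempting, and the documents support neither. A reader might infer that every extrapolated value is too high. The error multiplies the observed change, so it is zero for a subject without change and downward for one whose score fell.

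A reader might also infer that the excess falls on the E6011 arms alone, because placebo subjects switch at Week 24. That depends on a condition whose terms the SAP does not define:
- If treatment means agent, placebo-randomized subjects cannot be extrapolated from baseline across the switch.
- If it means dose, the 100 mg arm changes at Week 24 and the 400 mg arm at Week 12, which leaves mainly the 200 mg arm.
- If only the last film and the target week are compared, a placebo-randomized subject with a Week 52 film can be extrapolated to Week 76.

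**Conclusion.** The rule is wrong as written. With balanced brackets and first dose as origin, every non-zero forward-extrapolated change is too large in magnitude, because the time between the Screening film and first dose is left out. The excess is about 6% to 16% for a last film at Week 24 with s of 3 to 6 weeks, 3.4% or less for Week 52 to Week 76 with s up to 6, and near zero when the film is close to Day -1.

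A group mean is biased upward only if the mean observed change among imputed subjects is positive, which the documents do not state. The effect may differ by arm, but its pattern cannot be fixed until the same-treatment condition is defined. The number of imputed subjects is not given, so the effect on any summary cannot be sized. What is affected is limited to descriptive extension-phase summaries of mTSS, erosion and joint space narrowing, and the cumulative probability displays of mTSS change. The point is worth correcting because the bias comes from a stated rule and is cheap to remove.

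**What to change.** Replace the three formula lines in SAP 5.3.5 with one rule in balanced brackets:

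Value(W) = Post + (Post - Base) x (t_W - t_post)/(t_post - t_base)

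Here t_base and t_post are the actual radiograph dates and t_W is the first dose date plus 7W days. For s = 6, t = 24 and W = 52 the multiplier of the observed change is 1 + 28/30 = 1.933, as it should be. Apply the rule at Weeks 24, 52 and 76 and to the erosion and joint space narrowing scores. State the time origin for mTSS, and define what counts as the same treatment. SAP Table 8.12 places Week 52 at first dose plus 334 days, whereas 7 x 52 = 364, so the two need to be reconciled.

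The cost is SAP wording and one derivation. Study Day and the x-ray windows already require film dates, so no new data should be needed.

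An optional, separate refinement is to interpolate when films on the same treatment lie on both sides of the gap. As written, a missed Week 52 film is projected from earlier films even if a Week 76 film exists, so the imputed Week 52 score can exceed the observed Week 76 score.
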